The US Military is rapidly transitioning into preparing for multi-domain operations. Previous data demonstrates that the most common airway replaced in the prehospital combat setting is endotracheal intubation. Previous studies have suggested that video laryngoscopy (VL) is superior to direct laryngoscopy (DL), which is most prominently noted in novice users. However, the current durable equipment video laryngoscopes are very expensive and cost prohibitive for dispersion around the battlefield. The i-view is a novel video laryngoscope that is marketed for VL and is inexpensive and disposable. Both the durable VL and the i-view are already in use in our emergency department (ED). We are also already collecting data using these devices as part of an approved protocol for an airway registry. We are seeking to utilizing a clinical rotating protocol to compare these two devices in the emergency department.

B2. BACKGROUND AND SIGNIFICANCE

The emergency department (ED) at the Brooke Army Medical Center (BAMC) has collecting data under protocol C.2015.140 for an airway registry and is part of our routine business operations [1, 2]. The registry is primarily targeted at collecting data on every intubation that happens in the ED. Our department has been capturing data under this protocol for several years and all our staff are voluntarily providing case report form data. We will leverage the experience with this previous study to support this current protocol. We are seeking to conduct this study over-the-top of that protocol in the form of a clinical rotating protocol.

Effective prehospital interventions for combat injuries are critical for combat casualty survival. Airway compromise is the second leading cause of potentially preventable death in the prehospital, combat setting – second only to hemorrhage [3, 4]. Airway skills can be difficult to obtain and maintain for those in the prehospital combat setting [5]. The prehospital, combat environment is chaotic with significant challenges not present in the fixed-facility setting. Video laryngoscopy (VL) came about in the early 2000s. VL is a device that allows the operator to get a view of the intubating airway anatomy indirectly through a camera that projects

onto a monitor.[6, 7] While definitive evidence is lacking, observational evidence suggests that VL is superior to DL.[8, 9]

The US military forward stages the GlideScope® VL to many of the Role 2s and Role 3s, however, the Glidescope is not part of the sets, kits and outfits (SKO) for the Role 1 or Role 2 (without surgical team augmentation). However, the cost of acquiring this device has been cost prohibitive to push far-forward to all locations of care early in the chain-of-survival. A VL device is on the market – the i-view® (<https://us.intersurgical.com/info/i-view>) - which is fully disposable and single-use. The device costs approximately \$100 (USD) which is fraction of the cost of a GlideScope which the Army pays \$12,292.67 per device. (NSN 6515-01-572-7262, ZLIN Z05814) Moreover, it is one-time use and disposable. If an i-view device malfunctions or gets used in a far-forward area it is simply disposed of, whereas a Glidescope requires specialized skills to repair them if it malfunctions as well as proper cleaning equipment. Due to its inexpensive design, the i-view would be an ideal device to push to far-forward areas where maintenance, battery charging, repairs and stocking of accessories would become much less challenging.

In our department we routinely use VL devices for intubation including the reusable GlideScope and Storz systems. The i-view is disposable VL device and is already in use in our ED as part of routine clinical care.[10] This FDA-approved device is technically equivalent and we are using it in the FDA-cleared manner. However, it remains unclear whether it performs similarly in a pragmatic, clinical environment. We seek to determine if this device has similar performance characteristics in an emergency airway management setting.

B3. MILITARY RELEVANCE

Airway obstruction is cited as the second leading cause of potentially preventable death on the battlefield.[4] Relative to hemorrhage, there has been relatively little scientific development for airway management on the battlefield. Direct laryngoscopy is a challenging skill to develop and maintain which is a primary reason why it is not in the combat medic armamentarium. However, the advent of video laryngoscopy has significantly improved intubation success, likely side-stepping some of the skills required for direct laryngoscopy. Until now, dispersion of video laryngoscopes across the battlefield into the combat medic aid bags has been cost prohibitive. A new video laryngoscope, the i-view, is single-use and inexpensive – a potentially feasible technology for the far forward medical provider.

B4. OBJECTIVES/SPECIFIC AIMS/RESEARCH QUESTIONS

We are seeking to implement a clinical rotating protocol in which we will use alternating months for which VL device is to be used comparing the i-view to the reusable devices within our department.

We are seeking to answer the following questions:

- (1) Does the i-view have similar first pass success rates compared to the reusable VL devices (e.g. GlideScope, C-Mac)?
- (2) Does the i-view have similar attempts required for placement compared to the reusable VL devices?

B5. RESEARCH PLAN

B5.1 Research Design

We are seeking to conduct a **prospective study** comparing outcomes between the disposable i-view and our other reusable VL devices.

B5.2 Research Subjects/Population(s)

B5.2.1 Subject Population(s)

We are seeking all patients undergoing intubation for which the clinician **chooses** to use VL.

B5.2.2 Number of Subjects, Records, and/or Specimens

We are seeking all encounters for which a VL intubation happens over the course of 2 years. Our limit will be based on the number of times the procedure occurs. Based on previously published data, we are estimating ~200 intubations with 55% using VL per year based on our previous experience.[2]

B5.2.3 Inclusion Criteria

We are seeking any encounter for which the patient undergoes VL intubation as part of routine clinical care.

B5.2.4 Exclusion Criteria

No intubation will be excluded so long as VL is used.

B5.3 Research Procedures

Intubation Procedure	All intubations will be performed at the direction of the attending clinician. The decision to intubate is based purely on clinical factors by the primary team. The decision to use VL device will be at the direction of the clinical team. No patient will be recruited specific for this procedure.
Clinical Rotating Protocol	Currently in our emergency department, there are multiple VL devices that are already in use. These devices include the i-view as well as multiple reusable VL devices such as the GlideScope and the Storz C-Mac system. To ensure that we get high quality data, we are seeking to implement a clinical rotating protocol in which we will alternate months. For the clinical rotating protocol, one month will be the i-view and the next month will be the durable VL devices (e.g. January will be i-view, February will be the durable VL devices). As part of the clinical rotating protocol, we will place clinician-facing signage to the clinician work areas, on the airway boxes, and on the equipment in the department indicating which device is for that month if choosing to participate in the study. During the i-view month we may use a colored bag over the durable VL devices. Of note, our devices are routinely covered in a protective bag to keep it clean when not in use (e.g. aerosolized COVID, etc.) During the durable VL month we will place signs on the i-view device indicating that it is not an i-view month. We will use educational reminders to the staff about the protocol schedule and the purpose of the study throughout. We must note, however, the devices will remain in the department should the attending clinician need to break the protocol and obtain any of the devices. We will ensure that clinicians are able to access any of the equipment that they may want to utilize easily during emergent situations.
Data Collection	Data will be collected using the standardized data collection form that gathers routine healthcare data in a standardized form and ensures that the study team can identify intubations that occur. That information will then be linked to patient outcome data extracted by study team members.

B5.4 Data Collection

Data Element/Variable	Source	Operational Specific
Demographics, procedural data, complications, procedural operator data	Case report form	The data will be extracted into a Microsoft Excel database
Outcome data – Please see data variable collection appendix listed below	Case report form/T-system/trauma flow sheets/AHLTA/Impax/Essentris/MHS	The data will be extracted into a Microsoft Excel database

B5.5 Managing Data and/or Human Biological Specimens for this Research

Data will be documented using the enclosed case report form which is the same form already in use for BAMC protocol C.2015.140. This will ensure that our department personnel are already familiar with the documentation, the flow of documentation, and minimizing duplication of efforts. Upon completion of case report form, it will be combined with the data collection from the EMR and collated into a study database using Microsoft Excel using the same sequential numbering scheme. This dataset will be stored on government-issued computers and/or IMD-approved network shared drives available to the study team members. If data needs to be transmitted electronically, we will use official email communications or and approved file transfer system.

B5.6 Managing Data and/or Human Biological Specimens for Future Research

N/A – This section is not applicable

B5.7 Devices, Drugs, Dietary Supplements, Nutritional Supplements, And Biologics

B5.7.1 Devices

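### Eligibility is not tied to video laryngoscopy on the first attempt, although the powered endpoint is first-pass success

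*Combined protocol and SAP*

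**What the plan says.** Three parts of B5.2 define who is in the study.

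- B5.2.1 (Subject Population): "We are seeking all patients undergoing intubation for which the clinician" chooses VL.
- B5.2.3 (Inclusion): "We are seeking any encounter for which the patient undergoes VL intubation as part of routine clinical care".
- B5.2.4 (Exclusion): "No intubation will be excluded so long as VL is used".

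None of them says on which attempt VL must be used. Question 1 in B4 concerns first-pass success. Question 2 asks: "Does the i-view have similar attempts required for placement compared to the reusable VL devices". B8.1 sizes the study on first-pass success: 87% for the i-view, 92% for the reusable devices, a 5-point margin and 5% alpha. B5.8.2 tests it with the Farrington-Manning score test and a 90% interval, and drops an observation only when a value needed for that analysis is missing.

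The appendix collects the initial laryngoscope device type as free text. No eligibility or analysis rule refers to that variable.

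**The concern.** An encounter that starts with direct laryngoscopy, fails and is completed with VL satisfies B5.2.3 and B5.2.4. Its first pass was made with neither the i-view nor a reusable video device, so it carries no information about how either performs on a first pass. Its attempt count, which feeds question 2, includes an attempt made with a device outside the comparison. The missing-data rule does not remove it, because nothing is missing.

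Two things are at stake. First, a block of encounters that fail whichever video device follows moves both success rates away from 100%. That adds variance and shrinks any true difference between the devices. Second, if the block is larger in one group than in the other, it creates a difference that has nothing to do with the devices. The documents leave room for this. B5.3 says "The decision to use VL device will be at the direction of the clinical team", and the signage tells that team the device of the month before it chooses between direct and video laryngoscopy.

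**Working it through.** **The plan's own figure.** B8.1 gives a total of 122. With the stated inputs the expected deficit (92% − 87% = 5 points) equals the margin, so the distance to the margin is zero, no finite sample size exists, and power equals alpha. The figure of 122 does match the Farrington-Manning size per group with the two rates reversed (244 in total). That is a separate problem. The check below uses expected accrual instead.

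**Inputs from the documents.** B5.2.2: "we are estimating ~200 intubations with 55% using VL per year based on our previous experience", over 2 years. So 200 × 55% × 2 = 220 encounters, or about 110 per group (1:1 assumed from the alternating months). Margin 5 points; one-sided 5%; 87% v 92% as the true deficit at the margin. For equal devices, both are set at 92%.

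**Assumption.** A share r of included encounters are direct-first rescues, all scored as first-pass failures. The documents give no r. Shares of 5% and 10% of 220 are 11 and 22 rescues. If all 200 × 45% × 2 = 180 non-VL intubations are direct-first, that means 11/(180 + 11) = 6% and 22/(180 + 22) = 11% of direct-first cases being rescued with VL.

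**Formula.** Observed rates are p₁ = (1 − r₁) × i-view rate and p₂ = (1 − r₂) × reusable rate. Then

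P(claim) = Φ((p₁ − p₂ + 0.05)/SE − 1.645), with SE = √[p₁(1 − p₁)/n₁ + p₂(1 − p₂)/n₂].

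**No rescues, n = 110 per group.**
- 0.87 v 0.92: the numerator is 0, so P = Φ(−1.645) = 5.0%.
- 0.92 v 0.92: SE = 0.0366 and 0.05/0.0366 = 1.367, so P = Φ(−0.278) = 39%.

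**Equal rescue shares.**

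| r | Observed rates | Deficit seen | False claims | Equal-device power | n per group if restricted | Restricted: false claims | Restricted: power |
|---|---|---|---|---|---|---|---|
| 5% | 82.7% v 87.4% | 4.75 points | 5.6% | 30% | 104.5 | 5.0% | 38% |
| 10% | 78.3% v 82.8% | 4.5 points | 6.0% | 25% | 99 | 5.0% | 36% |

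Worked line for r = 10%, equal devices: both rates are 0.828, SE = 0.0509 and 0.05/0.0509 = 0.983, so P = Φ(−0.662) = 25%.

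**Unequal rescue shares (i-view v reusable), true deficit 5 points, n = 110.**

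| Shares | Observed rates | Deficit seen | False claims |
|---|---|---|---|
| 2% v 4% | 85.26% v 88.32% | 3.06 points | 11% |
| 5% v 10% | 82.65% v 82.80% | 0.15 points | 24% |
| 4% v 2% | 83.52% v 90.16% | 6.64 points | 2.2% |
| 10% v 5% | 78.30% v 87.40% | 9.10 points | 0.7% |

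Worked line for 5% v 10%: SE = 0.0510 and (−0.0015 + 0.05)/0.0510 = 0.951, so P = Φ(−0.694) = 24%.

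With both devices truly at 92%, a 5-point imbalance in rescues alone produces a difference of 0.92 × 5 = 4.6 points, nearly the whole margin. Restricting to first-attempt VL returns 5.0% false claims in every row, with 37% equal-device power for 5% v 10% in either direction.

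**Cross-check.** Simulating the Farrington-Manning test itself (400,000 runs per setting) gives false claims of about 5.6% and 6.2% and power of 29% and 26% for equal shares of 5% and 10%. The 5% v 10% imbalance gives 25%, and its reverse 0.7%.

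**The case against.** The plan may intend the narrower population. Choosing VL, in B5.2.1, can mean the device chosen at the outset. Question 1 asks about the i-view's own first-pass success, and the initial device is recorded. The case report form, which is not in the text reviewed, may record the device at each attempt. All of this stands as a possible reading, but no passage adopts it, and B5.2.4 is the broadest of the criteria. A field on a form would identify these encounters; it would not say what the analysis does with them.

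A reader might go further and infer that the plan scores rescues as failures against the i-view or the reusable devices. The documents do not say that. They define neither first-pass success nor how an outcome is attributed to a device. Scoring as failure is only the ordinary meaning of the term.

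The sizes also rest on assumed rescue shares. With equal shares the effect on false claims is small: 5.2% at a 2% share. The large figures need unequal shares, and no passage reports any. Finally, power is already only 39% with equal devices, and the sample-size contradiction matters more to whether the study can succeed. That is true, but correcting it would not settle which encounters belong in the first-pass analysis.

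**Conclusion.** The point holds as a mismatch between eligibility and endpoint. The criteria as written admit encounters whose first pass used neither study device, and no analysis rule removes them or says how to score them. If the rescue share is the same in both groups, at an assumed 5% to 10%, the cost is mainly power: 30–25% instead of 38–36% under the restriction, with false claims rising by one point at most. If the shares differ, the bias can run in either direction, and a gap of two points (2% v 4%) is enough to take false claims from 5% to 11%.

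It would be tempting to conclude that the comparison will be biased towards non-inferiority. The documents do not support that. They leave the choice of first device to a team that knows the month's device, which makes an imbalance possible, but they show neither that one exists nor which way it would go. These figures assume 110 per group, 87% v 92% (or both at 92%), and rescues scored as failures.

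**What to change.** Add to B5.2.3/B5.2.4 or to B5.8.2, before the data are seen:

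*The first-pass success and attempts analyses include only encounters whose first laryngoscopy attempt used VL. The device group for these analyses is never taken from a device used on a later attempt. Encounters begun with direct laryngoscopy and later managed with VL are counted and reported separately, by group.*

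Identify these encounters from the initial-device variable in the appendix, coded at data entry as i-view / GlideScope / C-Mac / direct / other. If the case report form already codes this, cite that field instead.

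The cost is a few sentences and one coded field, with no new data. If the rescues sit inside the 220, the groups fall to about 105 or 99 at 5% or 10% rescue, and power is still higher than with the rescues left in. If the 55% in B5.2.2 already counts only first-device VL, nothing is lost. The restriction does not remove selection in who receives VL first, which is why the rescue counts by group should be reported.

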We are not intending any direct interaction between study team members and subjects for the study with the exception of the clinical personnel. They may interact with the subjects only for routine healthcare and will not be for the purposes of this study. As we are requesting a HIPAA waiver and consent waiver, additional privacy for recruitment and such will not be required and standard measures for privacy will be maintained per usual methods for healthcare delivery. The data will be maintained and stored as outlined.

C5. CONFIDENTIALITY PROCEDURES FOR RESEARCH RECORDS, DATA, HUMAN BIOLOGICAL SPECIMENS

The hard-copy forms will be immediately deposited into a secured lock-box in the ED and destroyed by shredder once entered in the database(s). The data collection tool is password protected, encrypted. Regarding the component of the study using data to include the case report form, these will include minimal PHI in the form of a patient sticker that we routinely use for patient care labeling. The CRF data will be converted into an electronic database and linked with outcome data. Please see data variable collection appendix listed below. Data will be stored on a password-protected Excel database maintained on a government computer for the period of the study protocol. All of these forms will also be destroyed immediately after entry into the Excel database.

C6. RISKS OF HARM, MEASURES TO REDUCE THE RISKS OF HARM, AND BENEFITS OF PARTICIPATION

C6.1 Risks of Harm

No procedures or interventions are being performed because of this study. We are only seeking to answer a specific research question as part of a clinical rotating protocol using devices that are already in use and indicated for the same situations. While the critical nature of their illness and the mere need puts them at high risk as part of their routine medical care. We do not believe the use of a rotating protocol places them at additional risk. Moreover, clinicians can break the protocol if there is a specific clinical indication without any penalty.

C6.2 Incidental or Unexpected Findings

N/A – This section is not applicable. Unexpected or incidental findings are not expected as part of this study. If, in the unlikely event something is discovered, we will refer the information back to the primary attending clinician.

C6.3 Potential Benefits

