Was the patient on BIPAP or HFNC for respiratory failure in the 1 hour prior to enrollment (excluding pre-oxygenation)?	Yes/no
Was the patient on BIPAP or HFNC for respiratory failure in the 1 hour prior to enrollment (excluding pre-oxygenation)?	Optiflow, Vapotherm

Highest FIO2 delivered in the 1 hour prior to enrollment (excluding preoxygenation for the procedure).	For patients on nasal cannula, use estimation that $FIO_2 = 0.21 + 0.03^*(LPM\ of\ NC\ O_2)$
Neuromuscular Blockers	Rocuronium Vecuronium Succinylcholine Cisatracurium Other None Unknown
Total dose of each agent given peri-intubation	Numeric
Initial laryngoscope device type	Free text
Difficult airway characteristics (active at the time of intubation)	Vomiting Witnessed aspiration Upper GI bleeding Epistaxis or oral bleeding Upper airway mass, infection, trauma Head and neck radiation Obesity, BMI greater than 30 Limited neck mobility Limited mouth opening History of OSA Other, free text
Vital signs at 24 hours	Systolic blood pressure Diastolic blood pressure SPO2 FiO2 PEEP
Vasopressors or ionotropes used at 24 hours after intubation?	Epinephrine Norepinephrine Phenylephrine Dopamine WB Milrinone Angiotensin II
Is a chest x-ray available between intubation and 48 hours after intubation?	Was a NEW pneumothorax present on the first chest x-ray obtained in the first 48 hours after intubation? Is there evidence of new pneumonia? Yes/no
Cardiac arrest within 1 hour of intubation?	Yes/no
Death within 1 hour of intubation?	Yes/no
Did the patient die before discharge from the hospital?	Yes/no
Duration of mechanical ventilation (days)?	Number of days from study intubation until achieved final unassisted breathing during this hospitalization or death. Note: After extubation, a reintubation for less than 24 hours and for the purpose of a procedure will not count as a ventilator day. Information censored at hospital discharge. IGNORE data from outpatient records or readmissions.
Did the patient die in the ICU?	Yes/no
Duration of mechanical ventilation (days)?	Numeric
Duration of vasopressor support (days)	Numeric

ICU length of stay (days)	Numeric
---------------------------	---------

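### The plan does not show that reasons for breaking the monthly device schedule will be recorded, and does not say whether groups are formed by scheduled month or by device used

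*Combined protocol and SAP*

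**What the plan says.** B5.3 (Clinical Rotating Protocol) sets the schedule: "one month will be the i-view and the next month will be the durable VL devices". It also keeps every device within reach: "the devices will remain in the department should the attending clinician need to break the protocol and obtain any of the devices". C6.1 expects departures on clinical grounds: "clinicians can break the protocol if there is a specific clinical indication without any penalty".

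B5.5 says how this is documented: "Data will be documented using the enclosed case report form which is the same form already in use for BAMC protocol C.2015.140". C3 dates data collection under that registry protocol from 2015, before this rotation. C5 says the paper forms are shredded once entered in the database.

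The appendix contains "Initial laryngoscope device type", answered as free text, and a checklist headed "Difficult airway characteristics (active at the time of intubation"). It has no row for whether the scheduled device was passed over, or why. B5.4 assigns to the case report form "Demographics, procedural data, complications, procedural operator data".

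B5.8.2 names the Farrington-Manning test and allows regression adjustment as an option, without naming covariates. It does not define the two comparison groups when the device used differs from the device scheduled, and it does not commit to reporting departures.

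**The concern.** A calendar schedule protects the comparison only as far as it is followed, or as far as the analysis respects it. If harder airways in i-view months go to a reusable device, a comparison by device used gives the i-view an easier case mix and the reusable group a harder one. The estimate then moves in the i-view's favour, which is the direction that helps a non-inferiority claim. Departures for unrelated reasons, such as a missing or faulty device, habit, or not knowing the month, do not have this effect.

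The reason for each departure therefore bears directly on how far the device-used result can be trusted. A reason not written down at the time is unlikely to be recoverable, the more so because the paper forms are destroyed after entry. With the groups undefined as well, the choice between a steered and an unsteered estimate could be made after the data are seen.

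**Working it through.** **Inputs from the documents.** First-pass success 87% (i-view) and 92% (reusable), margin 5 points (B8.1). Expected volume 200 × 0.55 = 110 video intubations a year, so 220 in two years (B5.2.2), or about 110 per scheduled device. The stated total of 122 plays no part here.

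**Assumptions, not in the documents.** A fraction c of i-view-month encounters is moved to a reusable device, and none moves the other way. Cases moved for difficulty would succeed 65% of the time with the i-view and 70% with a reusable device, so the true difference is -5 points in these cases too.

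**Formulas.**
- i-view by device used = (0.87 - c × 0.65) / (1 - c)
- Reusable by device used = (110 × 0.92 + 110c × 0.70) / (110 + 110c)
- Difference by scheduled month = (0.87 - c × 0.65) + c × 0.70 - 0.92

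**c = 10%, moved for difficulty.**
- i-view: (0.87 - 0.065) / 0.90 = 89.4%
- Reusable: (101.2 + 7.7) / 121 = 90.0%
- By device used: -0.6 points
- By scheduled month: 0.805 + 0.070 - 0.920 = -4.5 points

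**c = 10%, moved for unrelated reasons.** Moved cases are average, so the device-used difference stays at 87 - 92 = -5.0. By scheduled month it is 0.9 × 0.87 + 0.1 × 0.92 - 0.92 = -4.5.

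**Other fractions, moved for difficulty, by device used.**
- c = 5%: 0.8375/0.95 - 105.05/115.5 = 88.2% - 91.0% = -2.8
- c = 15%: 0.7725/0.85 - 112.75/126.5 = 90.9% - 89.1% = +1.8

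**Opposite direction.** If 10% of reusable-month cases were instead moved to the i-view for difficulty, the reusable group would show (0.92 - 0.07)/0.90 = 94.4% and the i-view (95.7 + 7.15)/121 = 85.0%. The device-used difference would be -9.4. By scheduled month it would be 0.87 - (0.85 + 0.065) = -4.5.

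**Second illustration, equal devices.** Assume 20–40% hard airways, success of 94–95% in easy and 75–85% in hard airways, and 10–50% of hard airways in i-view months moved. The device-used comparison then favours the i-view by 0.3 to 5.0 points. At the upper end (40% hard, 95%/75%, half moved), hard cases make up 25% of the i-view group and 50% of the reusable group, giving 90.0% against 85.0%. The scheduled-month comparison shows no such bias.

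**Dilution.** With crossover c for unrelated reasons, the scheduled-month difference is the true difference × (1 - c): -5.0 becomes -4.5 at 10% and -3.5 at 30%.

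**Can outcomes alone reveal the reason?** At c = 10% about 11 encounters are moved. Expected successes are 11 × 0.70 = 7.7 if they were hard and 11 × 0.92 = 10.1 if ordinary. The binomial standard deviation in the first case is √(11 × 0.7 × 0.3) = 1.5. The gap between the two analyses is a hint, not a clear answer.

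**The case against.** The case against has real force, and several parts of it stand.

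- **The form has not been seen.** B5.5 calls it enclosed, but it is not in the text supplied. The appendix is not the whole form: it does not list first-pass success or number of attempts either, although those are the study questions in B4. A reader might infer that the reason is definitely not captured. The documents do not support that. They support only that nothing in them shows it will be, and that a form older than the schedule is unlikely to ask.
- **The data are not helpless without the reason.** A reader might infer that the data could never tell a real device difference from steering. That also goes too far. Departures can be identified from date and device, assuming the intubation date is retained. The scheduled-month contrast needs no reason: it is -4.5 in each 10% scenario above. The difficult-airway checklist, BMI, active conditions and operator data allow kept and moved encounters to be compared.
- **Free text is a minor matter.** A reader might infer that a free-text device field undermines the grouping. Three devices are named in the protocol, and coding them as i-view or reusable is routine.
- **The direction is assumed.** Steering could run the other way, and the calculation above shows that it would then count against the i-view.

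The remaining gap is narrower. The checklist says how difficult the airway was, not why the scheduled device was passed over. B5.8.2 does not commit to the scheduled-month analysis that would avoid the problem, and adjustment is optional.

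**Conclusion.** The point holds in limited form and is worth acting on before the rotation starts. The plan expects departures, does not show that their reasons are recorded, and does not say which grouping the non-inferiority test uses. Under the stated assumptions, difficulty-driven departures in 5% to 15% of i-view-month encounters turn a true -5.0 into anything from -2.8 to +1.8 by device used. That shift is large against a 5-point margin. The scheduled-month estimate stays near -4.5, at the price of some dilution.

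These sizes rest on an assumed departure rate, assumed success in moved cases, and departures in one direction only; the documents give none of these. A reason item would not settle the grouping question by itself. Nor would it address selection through the choice of video laryngoscopy, which is made when the month's device is already known and which determines who enters the study.

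**What to change.** 1. Check what the enclosed form asks. If it has no such item, add one before the rotation starts: *Scheduled device used first? If no, main reason: anticipated difficult airway / device unavailable or faulty / operator preference / not aware of schedule.*
2. In B5.8.2, commit to reporting first-pass success both by scheduled month and by device used.
3. Tabulate departures by reason and by scheduled month, and compare the difficult-airway items between kept and moved encounters. With perhaps 11 departures at a 10% rate, this would be descriptive.
4. State without condition that the device-used comparison alone will not support a non-inferiority claim. A rule triggered only when difficulty-driven departures occur would need a threshold.
5. Optionally, replace the free-text device field with a closed list.

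The cost is one revised form page, a few more seconds per form, a form slightly different from the registry's, and one added table. The scheduled-month estimate is diluted by crossover, so the departure rate should be shown beside it.
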